5.2.3 Day 29 Postvaccination Procedures ("not previously vaccinated" subjects)

After confirming subject continues to meet study eligibility criteria by completing procedures outlined in [Section 5.2.2, Day 29 Prevaccination Procedures \(not previously vaccinated subjects\)](#) above, perform vaccination of the subject according to the assigned study vaccine and according to the procedures described in [Section 6, Treatment of Subjects](#).

The following postvaccination procedures should be carried out on Day 29:

1. Careful re-training, if necessary, of the subject's parent(s)/LAR(s) on how to measure local reactions and body temperature, how to complete and how often to complete the Subject Diary Card is crucial. Reference [Section 5.2.1, Day 1 Postvaccination Procedures \(All Subjects\)](#) for Subject Diary Card instruction. Any re-training must be recorded in the source documents.
2. After vaccination, the subject will be observed for at least 30 minutes including observation for local and systemic adverse events, AEs, and body temperature measurement. Please take the opportunity to remind the subject's parent(s)/LAR(s) how to measure solicited adverse events and body temperature as part of this observation period. Record all safety data collected in the source documents. **The 30-minute observation data must be recorded in the source documents only; not in the Subject Diary Card.**
3. Schedule/review the next study activities, reminder telephone calls, and clinic visit, with the subject's parent(s)/LAR.

Remind the subject's parent(s)/LAR(s) to complete the Subject Diary Card daily and to contact the site if there are any questions and to contact the site immediately (or as soon as the subject is medically stable) if the subject has a medical condition that leads to a hospitalization.

5.2.4 Postvaccination Reminders

Reminder calls or alerts are not intended to be an interview for collection of safety data. If the subject's parent(s)/LAR(s) wishes to describe safety information, this information should only be collected by a healthcare professional at the site, and the safety data described must be written down in the subject's medical chart.

Subject Diary Card Reminder Calls

Subject Diary Card reminder calls will be performed on Day 3 (all subjects) and Day 31 ("not previously vaccinated" subjects). The purpose of this call is to remind the subject's parent(s)/LAR(s) about completion of the Subject Diary Card. The call follows the Subject Diary Card Reminder Telephone Call Script provided to the site. The subject's parent(s)/LAR(s) should be reminded to contact the site to discuss medical questions.

5.3 Postvaccination Visits

Postvaccination visits (clinic visit or safety assessment call) will be performed on Days 29, 91 and 181. ("previously vaccinated" subjects) or on Days 57, 119 and 209 ("not previously vaccinated" subjects). In the event that a scheduled or unscheduled visit or call coincides, procedures may be combined.

5.3.1 Postvaccination Clinic Visits

The following procedures will be performed on Day 29 for "previously vaccinated" subjects and on Day 57 for "not previously vaccinated" subjects:

1. At the clinic visit, the Subject Diary Card will be reviewed. Please see [Section 3.4.2, Tools used for Data Collection](#) for additional guidance on Subject Diary Card review. If any other adverse events are reported, this should be discussed with a qualified health care professional.

The subject's parent(s)/LAR will be interviewed to determine if any unsolicited adverse events (including medically attended AEs, SAEs and AEs leading to study or vaccine withdrawal) occurred and if any concomitant medications or vaccines were taken/received in the time since the last clinic visit. The qualified health care professional reviewing these data will discuss the symptoms (if any) reported by the subject and will determine if any additional diagnoses and/or adverse events are present. Adverse events

reported by the subject's parent(s)/LAR at this follow-up clinic visit must be recorded in the subject's source document and on an Adverse Events eCRF, as specified in [Section 7.1, Safety Assessment](#).

2. Perform a review of organ systems by interview that queries the subject's parent(s)/LAR(s) as to any complaints the subject has experienced across each organ system. This will be used to guide the physical examination. Corresponding information is documented in the subject's source documents.
3. Blood will be drawn (approximately 8 mL) from all subjects for serology testing. Details regarding the volume of blood and testing to be performed are in [Section 3.5, Collection of Clinical Specimens](#).
4. Schedule safety telephone calls on Days 91 and 181 for "previously vaccinated" subjects and on Days 119 and 209 for "not previously vaccinated" subjects.

Remind the subject's parent(s)/LAR(s) to contact the site if there are any questions and to contact the site immediately (or as soon as the subject is medically stable) if the subject has a medical condition that leads to a hospitalization or an emergency room visit.

5.3.2 Safety assessment calls

Safety assessment calls will be performed on Days 91 and 181 (previously vaccinated subjects) or Days 119 and 209 (not previously vaccinated subjects).

Safety assessment calls are calls made to the subject's parent(s)/ LAR by a qualified healthcare professional designated on the site log. These calls will follow a script which will facilitate the collection of relevant safety information. The subject's parent(s)/LAR(s) will be interviewed according to the script. Safety assessment calls performed on Days 91 and 181 (previously vaccinated subjects) or Days 119 and 209 (not previously vaccinated subjects) will collect information relating to a subset of unsolicited adverse events including SAEs, NOCDs, AEs leading to withdrawal, and concomitant medications or vaccinations associated with those events. All safety information described by the subject's parent(s)/LAR(s) must be written down in a designated location within the source document and not written on the script used for the telephone call.

The subject's parent(s)/LAR(s) will be asked as to whether the subject was hospitalized or was evaluated at an emergency room for any illness since the site's last contact with the subject. If an SAE has been identified by the site staff during the interview which has not previously been reported by the subject's parent(s)/LAR, this SAE will be reported by the site within 24 hours to Seqirus or delegate. Any additional relevant medical history will be reported to Seqirus or delegate and recorded as needed.

The subject's parent(s)/LAR(s) will receive a reminder of the next planned study activity, if applicable. The subject's parent(s)/LAR(s) will be reminded to contact the site immediately (or as soon as the subject is medically stable) if the subject has a medical condition that leads to a hospitalization or an emergency room visit or to a visit to/by a doctor or is otherwise of concern.

5.4 Unscheduled Visit(s)

An unscheduled study visit may be performed as necessary for further evaluation of safety information that is described on the telephone that is to be investigated further at any time during the study.

5.5 Study Completion Visit

Study completion will occur 180 days after last vaccination. For all subjects, the termination visit is a telephone call performed by a qualified health care professional.

The study completion visit will coincide with the safety call on Day 181 (previously vaccinated subjects) or Day 209 (not previously vaccinated subjects). The date of completion is the date of the last contact (telephone call) in which the subject's health status was assessed or, in cases where the subject's parent(s)/LAR(s) does not agree to any further safety follow-up, it is the date consent is withdrawn. This date should be recorded on the Study Completion CRF page. For visit procedures to be performed for a subject whose planned study participation ends prematurely, please see [Section 5.5.1, Early Termination Visit.](#)

At the Study Completion Visit, the following procedures will be performed:

- Interview the subject's parent(s)/LAR(s) to obtain information regarding potential SAEs, NOCDs, and AEs leading to withdrawal and the medication to treat these
- Ask the subject's parent(s)/LAR(s) as to whether the subject was hospitalized or was evaluated at an emergency room for any illness since the site's last contact with the subject. If an SAE has been identified by the site staff during the interview and has not previously been reported by the subject's parent(s)/LAR(s), this SAE must be reported by the site within 24 hours to Seqirus or delegate. Record any additional relevant medical history as needed.

The site will review with the subject's parent(s)/LAR(s) the plan of when information relating to the subject's participation in the study may be available (eg, study results). It will also be discussed how information relating to the subject's participation in the study will be shared with the subject's healthcare provider, if the subject's parent(s)/LAR(s) chooses to share this information.

The site will complete the study completion eCRF page and this will mark the completion of the subject's participation in the study.

5.5.1 Early Termination Visit

When a subject is withdrawn from treatment or withdraws from the study, the Investigator will notify the Sponsor and, when possible, will perform the procedures listed below. The reason(s) for the early termination will be included in the subject's source documentation. If the Early Termination Visit is a telephone call, collect as much information as possible. Early Termination Visits include subjects who were randomized but not treated.

At the clinic visit or during the telephone call, the same procedures will be performed as during the study completion visit, see [Section 5.5, Study Completion Visit](#), if possible.

In addition, the following procedures will be performed:

- Collect and review Subject Diary Card, if applicable.
- Review the subject's safety data (if collection of these was in progress at the time of study completion).

The site will review with the subject's parent(s)/LAR(s) the plan of when information relating to the subject's participation in the study may be available (eg, study results, treatment assignments). It will also be discussed how information relating to the subject's participation in the study will be shared with the subject's healthcare provider, if the subject/subject's parent(s)/LAR(s) chooses to share this information.

The site will complete the termination eCRF page and this will mark the completion of the subject's participation in the study.

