3.8 Premature Withdrawal From Study

A subject may withdraw at any time, or be dropped from the study at the discretion of the Investigator should any untoward effects occur and/or for safety reasons. In addition, a subject may be withdrawn by the Investigator or the Sponsor if he/she violates the study protocol and/or related procedures. The Investigator or study coordinator must notify the Sponsor immediately when a subject has been withdrawn due to an adverse event.

The circumstances above are referred to as premature withdrawal from the study, and the reason for premature withdrawal should be clearly documented and detailed in the source documentation. The Investigator should make every attempt to evaluate the subject's safety, including resolution of ongoing AEs, at the time of premature withdrawal. If a subject's parent(s)/LAR(s) wants to withdraw the subject from the study before all doses are administered or prior to the last planned study visit, the subject's parent(s)/LAR(s) will be asked to be followed for safety for the duration of the study. When a subject is withdrawn from the study, the procedures described in [Section 5.5.1, Early Termination Visit](#) should be completed whenever possible.

The reasons for premature withdrawal from the study include adverse event, death, withdrawal of consent, lost to follow-up, other, and protocol deviation. These reasons are described in greater detail below.

Adverse Event

For any subject withdrawn from study participation prior to the planned Study Completion Call, it is important to determine if an AE was associated with the reason for discontinuing the study. This AE must be identified on the Adverse Event eCRF page by indicating "Withdrawn from study due to AE." Any ongoing AEs at the time of study withdrawal must be followed until resolution or stabilization.

Subjects who develop an SAE judged to be possibly or probably related to the study vaccine, including hypersensitivity reactions, should not receive subsequent vaccination.

If a medically-attended adverse event occurred, the event should also be reported on the Adverse Event eCRF page (see [Section 7.1, Safety Assessment](#)).

Death

For any subject withdrawn from study participation due to death, this should be noted on the Study Completion eCRF and the associated SAE that led to the death must be reported on the SAE page.

Withdrawal of consent

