Prior to receipt of second study vaccination, subjects must be evaluated to confirm that they are eligible for subsequent vaccination. If subjects meet any of the original exclusion criteria listed above or experienced severe tolerability issues after first study vaccination, they should not receive additional vaccinations. However, these subjects should be encouraged to continue study participation. This review of eligibility should be documented in the source document and the reason for not administering a scheduled study vaccine should be documented in the eCRF.

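### Section 5.5.1 applies the Early Termination Visit, which has no blood draw and ends participation, to withdrawal from treatment, while Section 4.2 encourages a child who may not have dose 2 to stay in the study.

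*Protocol*

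**What the plan says.** - **Section 5.5.1.** The trigger is "When a subject is withdrawn from treatment or withdraws from the study, the Investigator will notify the Sponsor". At the visit or call, "the same procedures will be performed as during the study completion visit": an interview on SAEs, new chronic diseases and AEs leading to withdrawal, with a question about hospital or emergency care. Diary collection and a safety data review are added. No blood draw is listed. The section ends: "The site will complete the termination eCRF page and this will mark the completion of the subject's participation in the study".
- **Section 4.2, closing paragraph.** A child who meets an exclusion criterion on recheck, or who tolerated dose 1 badly, is not vaccinated again. The text then adds: "However, these subjects should be encouraged to continue study participation". The reason for withholding the dose goes in the eCRF. Section 5.2.2 also asks for the reason and says nothing of termination.
- **Section 3.8.** Parents who want to take a child out before all doses are given "will be asked to be followed for safety for the duration of the study". The pointer to 5.5.1 sits in a sentence beginning "When a subject is withdrawn from the study, the procedures described in", so it concerns leaving the study.
- **Section 5.5.** It refers to 5.5.1 for a child whose planned participation stops early. It also says: "Study completion will occur 180 days after last vaccination".
- **Schedule and endpoint.** In children not previously vaccinated, Section 5.3.1 draws blood from all of them at Day 57. Table 1-2 counts V3 to V5 from V2. The third safety endpoint in Section 8.1.2.1 runs from Day 1 to Day 209.

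**The concern.** Stopping vaccination and leaving the study are different events. Section 7.1.3 names them separately, and Section 3.8 distinguishes complete withdrawal from staying on for safety. Section 5.5.1 gives both the same consequence. When dose 2 is withheld at Day 29, a site can find support for closing the child out (5.5.1) and for encouraging the child to stay (4.2). Section 3.8 allows no authorised deviations, so the text has to be unambiguous.

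Two kinds of data depend on the choice: the Day 57 sample and the safety follow-up after Day 29. Severe tolerability problems after dose 1 are among the reasons for withholding dose 2, so the children lost may differ from those who remain, and the loss may vary by site.

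**Working it through.** The plan gives no figure for this event, so the check compares the texts and counts days.

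**1. One child, two routes.** Take a child not previously vaccinated whose dose 2 is withheld at V2 (Day 29).
- Under 5.5.1, if the site regards this as withdrawal from treatment: completion interview, diary and safety review, no blood, termination form, participation over.
- Under 4.2: reason recorded and the child encouraged to continue. If the child stays, Table 1-2 provides V3 with blood and two safety calls.

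**2. Which sections agree.** Sections 3.8 and 5.5 tie 5.5.1 to the end of study participation. Sections 4.2 and 5.2.2 do not send the child with a withheld dose there. Only 5.5.1's own opening sentence adds withdrawal from treatment.

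**3. Serology.** The Evaluable Set (Protocol 8.3.4), renamed FAS Immunogenicity in the SAP (4.4), needs vaccine on Day 1 and valid results at Day 1 and, for this group, Day 57. Receipt of dose 2 is not among its listed conditions. A child who stays can therefore qualify on those conditions; a child closed out at Day 29 cannot. SAP 5.2 treats missing titers as missing completely at random, without imputation. The exploratory missing-data analysis (SAP 6.5.1.3 and Appendix C) is run on the PPS, which is a subset of FAS Immunogenicity (SAP 4.5). It cannot bring back a child with no Day 57 result.

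**4. Safety follow-up lost by closing out at Day 29.**
- Calendar to Day 209: 209 − 29 = 180 days; 180/209 = 86%.
- Calendar to Day 181: 181 − 29 = 152 days; 152/181 = 84%.

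The size barely depends on which calendar applies.

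**5. Timing if the child stays.** With V2 at Day 29, Table 1-2 gives 29 + 28 = Day 57, 29 + 90 = Day 119 and 29 + 180 = Day 209. Where the text counts from the last vaccination, which for this child was on Day 1, the same intervals give Days 29, 91 and 181.

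**6. Number of children.** This would need the share of children on the two-dose schedule, the proportion with dose 2 withheld, and the proportion of those closed out under 5.5.1. The documents give none of them. The drop-out allowance, 2418 − 2175 = 243 children, is not broken down by reason.

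**The case against.** The strongest reply is that Section 4.2 already has a specific rule for this child, and that neither 4.2 nor 5.2.2 calls the child withdrawn from treatment. On that view 5.5.1 contains one loose phrase against several consistent sections. This stands in part: it takes a site's reading to trigger 5.5.1. But the phrase is in the current text and withholding the remaining dose is a natural reading of it.

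A reader might infer several stronger points that the documents do not support:
- **Section 3.8 keeps the child for serology.** It concerns a parent who wants to leave, it asks rather than requires, and it covers safety only. The Day 57 conflict rests on 4.2 and 5.3.1 against 5.5.1.
- **The follow-up calendar is unworkable.** Days 57, 119 and 209 attach to the not-previously-vaccinated group, which is defined by history, and V2 can take place without a dose. SAP Appendix A calls its matching chart binding where the protocol appears inconsistent. That largely answers the point, although the precedence rule is in the SAP, not in the protocol that sites follow.
- **The loss is informative.** It may be. Dose 2 can also be withheld for reasons unrelated to reactions, such as another vaccine, another trial or expected non-compliance.
- **The primary analysis is affected.** Neither document says outright whether a missed dose 2 excludes a child from the PPS. SAP 4.5.1 lists incorrect dose and missed key procedures as deviation categories, which leaves it open.
- **A head count can be given.** Any figure would rest on rates from outside the documents. Counting every child with dose 2 withheld would also give only a ceiling, because some would stay.

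**Conclusion.** The conflict is real and worth correcting, within limits. As written, 5.5.1 allows a site to end the participation of a child whom 4.2 wants encouraged to stay. For each child closed out at Day 29 the cost is the Day 57 sample and 180 of 209 days (86%) of SAE and new-chronic-disease follow-up, or 152 of 181 days (84%) on the shorter calendar. This assumes that the site treats a withheld dose 2 as withdrawal from treatment and that the child would otherwise have completed the schedule.

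The parts of the plan clearly exposed are the supporting Evaluable/FAS Immunogenicity analysis and the third safety endpoint. The loss may be selective. Its frequency is unknown, and no effect on the PPS conclusion or on power is shown.

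**What to change.** Reconcile 5.5.1 with 4.2, 3.8 and 5.5, for data collection only:
- Word 5.5.1 so that the Early Termination Visit and termination form apply to children who leave the study.
- State in 5.2.2 and a Table 1-2 footnote that a child who misses dose 2 but stays keeps the contacts already scheduled there. Any blood draw remains subject to the existing eligibility and safety criteria; exclusion criterion 3, rechecked before dose 2, covers contraindications to blood draws.
- Reconcile, for this child, Table 1-2's counting from V2 with the wording that counts from the last vaccination, so that serology and safety calls have one stated calendar.

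This takes no position on who receives dose 2. The cost is a few words and a footnote. The downside is a few more already scheduled contacts for children who might otherwise have been closed out; no new visit type or procedure is added.

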6. TREATMENT OF SUBJECTS

All vaccines associated with this study are to be stored separately from other vaccines and medications in a secure location under appropriate storage conditions with temperature monitoring. **All vaccines associated with this study must be checked for expiration date prior to use. Expired vaccines must not be administered to subjects.**

6.1 Study Vaccine(s)

The term 'study vaccine' refers to those vaccines provided by the Sponsor or delegate, which will be evaluated as part of the study objectives. The study vaccines specific to this study are described below.

QIVc

An approximately 0.5 mL dose of QIVc (cell-derived seasonal quadrivalent influenza vaccine) contains nominally 15 µg of hemagglutinin (HA) of each of the 2 influenza type A strains and each of the 2 influenza type B strains for a total of 60 µg of HA in the vaccine. The strain composition will be that recommended by the WHO, Center for Biologics Evaluation and Research (CBER), and Committee for Medicinal Products for Human Use (CHMP) for quadrivalent influenza vaccines contemporaneous to the timing of the study. The full composition of the vaccine is reported in [Table 6.1-1](#).

Table 6.1-1 QIVc Vaccine Composition

Names of Ingredients	Quantity per Dose* (0.5 mL/Dose)	Function
Active Ingredients Hemagglutinin (HA) and Neuraminidase (NA) antigens from the influenza virus strains recommended by the WHO / CBER/ CHMP for the respective season Strain A1 Strain A2 Strain B1 Strain B2	≥ 15µg HA (per strain)	Influenza Vaccine
Other Ingredients		
Buffer M (PBS) pH 7.2 sodium chloride potassium chloride magnesium chloride hexahydrate disodium phosphate dihydrate potassium dihydrogen phosphate	[REDACTED]	Isotonic aid Isotonic acid Stabilizer Buffer Buffer
Water for injection	Up to 0.5 mL	diluent

Abbreviations: CBER = Center for Biologics Evaluation and Research; CHMP = Committee for Medicinal Products for Human Use; HA = hemagglutinin; mg = milligrams; mL = milliliters; µg = micrograms; NA = neuraminidase; QIVc = cell-based quadrivalent influenza vaccination; WHO = World Health Organization

* the quantities indicated in this table reflect the amount in a 0.5 mL dose.

** each dose of Flucelvax Quadrivalent may contain residual amounts of β-propiolactone (<0.5 µg), cetyltrimethylammonium bromide (≤18 µg), polysorbate 80 (≤1500 µg), MDCK cell protein (≤8.4 µg), protein other than HA (≤240 µg), MDCK cell DNA (≤10 ng), which are used in the manufacturing process. The 0.5 mL pre-filled syringes (PFS) contain no preservative or antibiotics.

US-licensed QIV comparator vaccine:

Afluria Quadrivalent® inactivated influenza virus vaccine

Afluria Quadrivalent® will be used as a US-licensed QIV comparator vaccine.

Afluria Quadrivalent® is an inactivated influenza virus vaccine for intramuscular injection. Afluria Quadrivalent® is supplied in a 0.25 mL and a 0.5 mL pre-filled syringe (PFS). For children 6 months through 35 months of age, 0.25 mL dose of vaccine will be administered. For children 36 months through 47 months of age, 0.5 mL will be administered.

For a comprehensive review of Afluria Quadrivalent® please refer to the United States Product Information (USPI) supplied by Seqirus or delegate; this document should be reviewed by the Investigators prior to initiating the study.

